11.9. Statistical Considerations for the Open-Label Extension Period

The objectives of the Open-Label Extension Period are to evaluate long-term safety, tolerability, and efficacy up to 52 weeks for eligible subjects who complete the 12-week Double-Blind Treatment Period and the Safety Follow-Up Visit 4 weeks after last dose of study treatment. All subjects will receive 2 mg etrasimod treatment during Open-Label Extension Period.

No pair-wise comparison will be performed. Only descriptive statistics will be provided and details will be discussed in the SAP.

Analysis sets: all safety outcomes will be analyzed in Safety Set which includes all subjects who receive at least 1 dose of etrasimod. Efficacy outcomes will be summarized in efficacy evaluable set which includes subjects who receive at least 1 dose of etrasimod and have at least 1 efficacy measurement during the Open-Label Extension Period; therefore, efficacy evaluable set is endpoint specific.

Baseline for the Open-Label Extension Period is defined as the last measurement prior to the first etrasimod dose started at Week 16.

Safety analyses will follow general considerations in Sections 11.8.1 to 11.8.7 with following exceptions:

- 1 treatment group in the Open-Label Extension Period and 3 subgroups in the Double-Blind Treatment Period will be analyzed
- the Open-Label Extension Period visits will follow [Table 9](#) in [Appendix 1](#)

- change from baseline will be analyzed on change from Double-Blind Treatment Period baseline, and change from Open-Label Extension Period baseline, respectively

Efficacy outcomes will be measured at scheduled visits in the Open-Label Extension Period: EASI, vIGA, SCORAD, BSA, Pruritus NRS, POEM, DLQI, and PGA (Table 9 of Appendix 1). Dichotomous response outcomes derived from specific scores will be assessed. Continuous variables will be summarized by visit using the number of observations, mean, SD, median, minimum, and maximum; and categorical variables will be summarized by visit using frequency counts and percentages, with following considerations.

- 1 treatment group in the Open-Label Extension Period and 3 subgroups in the Double-Blind Treatment Period will be analyzed
- change from baseline in continuous variables will be analyzed on change from Double-Blind Treatment Period baseline, and change from Open-Label Extension Period baseline, respectively

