Statistical analysis will be performed following IQVIA Biotech standard operating procedures and on the IQVIA Biotech computer network. All statistical analysis will be performed using SAS Version 9.4 with program code prepared specifically for the project by qualified IQVIA Biotech statisticians and SAS programmers.

All observed and derived variables (e.g., change from baseline, percentage change from baseline, and response status) that are analyzed or summarized will be listed by subject. Descriptive statistics will provide an overview of the efficacy and safety results. For categorical parameters, the number and percentage of subjects in each category will be presented. For continuous parameters, descriptive statistics will include number of subjects, mean, SD median, minimum, and maximum.

B. Definition of Baseline and Study Day

Study day will be defined separately for the DB Treatment Period and OLE Period. For all subjects, Day 1 is the date of first study drug administration in the DB Treatment Period. This will be referred to as the **Overall Day 1**. For those enrolling into the OLE Period, an **OLE Day 1** will be additionally defined as the date of the first study drug administration in the OLE Period at Week 16.

Study day will be calculated relative to the date of Overall Day 1.

Similarly, Baseline will be defined separately for DB Treatment Period and OLE Period as follows:

[figure not shown]
- **DB Treatment Period:** baseline will be defined as the last available measurement prior to the first dose of the study drug in DB Treatment Period. Specifically, for vital signs (resting heart rate (HR), blood pressure (BP), body temperature, and respiratory rate) and [REDACTED], the Day 1 pre-randomization assessments will be used as baseline measurements. The lowest pre-dose HR measurement will be used for comparison to the post-dose HR measurement. This will be referred to as the **DB baseline**.

[figure not shown]
- OLE Period: for those enrolling into the OLE Period, an **OLE baseline** will be additionally defined as the last pre-dose measurement at Week 16 at Week 16.

Change from baseline is defined for both DB Treatment Period and OLE Period as the post-baseline value minus the baseline value unless otherwise specified. Percent change from baseline is calculated as follows: Percent change = (Change from baseline / Baseline) x 100.

C. Analysis Visit Window

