- TEAEs by SOC, PT, and maximum Common Terminology Criteria for Adverse Events (CTCAE) severity
- TEAEs by SOC, PT, and maximum relationship to the study treatment
- Non-serious TEAE by SOC and PT

Targeted Medical Events by PT and Category will be summarized for DB Treatment Period, OLE Period, and overall.

All AEs will be presented in a by-treatment, and by-subject listing, for the DB treatment and OLE Periods separately, detailing the verbatim term given by the investigator, the PT, SOC, onset date, end date, CTCAE grade, outcome, relationship to study treatment, action taken with study drug, other action taken, seriousness and criteria for seriousness. SAEs and AEs leading to study treatment discontinuation will also be presented in a separate listing.

D. Clinical Laboratory Results

Laboratory parameters from the central laboratory will be summarized by treatment group at each scheduled assessment time point. For continuous lab parameters (hematology, serum chemistry, coagulation, and urinalysis), absolute values and change from Baseline will be summarized using descriptive statistics. For the OLE Period, change from Baseline will be calculated for the DB baseline and OLE baseline separately. Associated laboratory parameters (e.g., hepatic

[REDACTED]

enzymes, renal function, and hematology) will be grouped and presented together.

Changes from Baseline in the out of reference range abnormality flags will also be summarized using shift tables at each post-Baseline visit.

Data listings by-treatment and by-subject will be provided for all laboratory parameters reported in the standard units provided by the central laboratory. Lab values outside of the standard reference range will be noted.

Local laboratory assessments will be displayed in a separate listing. Pregnancy test results will be listed.

E. Vital Signs

Descriptive statistics for absolute values and change from Baseline in vital signs (BP, HR, respirations, body temperature) will be presented by treatment group. For OLE Period, change from Baseline will be calculated for the DB baseline and OLE baseline separately.

At baseline and week 16, descriptive statistics for pre-dose measurements and change of vital signs values will be presented by treatment group [REDACTED] after treatment initiation. [REDACTED]

[REDACTED]

[REDACTED]

[REDACTED]

[REDACTED]

[REDACTED]

[REDACTED]

[REDACTED]

[REDACTED]

[REDACTED]

G. Physical Examination

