Individual subject plasma concentrations will be plotted (in both linear and semilogarithmic scales) versus actual time from start of treatment, for timepoints in DB Treatment Period (Baseline/Day 1 to Week 16) and for timelines in OLE Period (Week 16 to 72), separately.

C. Steady-State (SS) Concentration Analysis

Steady-state (SS) concentration will be assessed for the DB Treatment Period and OLE Period separately. Individual subject SS pre-dose (trough) plasma concentrations will be averaged across ($C_{ss,avg\ trough}$) across the timeframe shown by the statistical model to be steady state; for the DB portion, out to a maximum timeframe of 12 weeks, and in the OLE out to a maximum of 68 weeks. Only C_{trough} values in the range of steady state will be averaged into $C_{ss,avg, trough}$. Individual SS pre-dose concentrations will be included in the data listings and summarized using descriptive statistics as described above for DB Treatment Period and for OLE Period separately (except with respect to scheduled nominal time which is not applicable).

Box plots of SS pre-dose (trough) plasma concentrations will be plotted versus scheduled nominal time for each scheduled nominal visit, by treatment received in DB Treatment Period and overall.

Box plot of $C_{ss,avg\ trough}$ will be plotted by treatment received in DB Treatment Period and overall.

Scatter plot matrices, stratified by treatment, of individual subject $C_{ss,avg\ trough}$ values versus baseline body weight and age will also be plotted, and showing correlation coefficient (Spearman's rank correlation coefficient) and p-value.

Etrasimod plasma steady-state will be determined by regressing trough (pre-dose) concentration values over time for the DB Treatment Period (Baseline/Day 1 to Week 16) and OLE Period (Week 16 to Week 72) separately and the resultant slope will be tested for its difference from zero. For each treatment period, a set of data ranged by weeks will be fitted using a mixed effect model with Treatment group (for DB Treatment Period) and week (as a continuous covariate) as fixed effect terms and subject as a random effect term. Steady state is estimated to be achieved as the earliest week included in the analysis when the 90% CI of the slope includes 0.

D. Exposure-Response Relationship Analysis

To explore potential etrasimod plasma exposure-response relationships, the following will be generated, and Baseline below refers to DB Baseline:

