- Scatter plot matrix of individual subject change from baseline in EASI Score at Week 12 values versus corresponding individual subject pre-dose (trough) concentrations at Week 12, and showing correlation coefficient r - and p-value (Spearman's rank correlation coefficient). The same approach will also be used to generate another set of similar scatter plots but using instead

individual subject $C_{ss,avg}$ trough concentrations (rather than Week 12 predose concentrations).

█ [REDACTED]

█ [REDACTED]

- Overlay plot showing profiles of mean (SD) heart rate absolute change from baseline (first dose cardiac monitoring) and mean (SD) plasma concentration versus scheduled nominal time from start of treatment for Day 1 will be plotted by DB treatment. A similar set of overlay plots will also be generated instead using mean (SD) heart rate (beats/min) and mean (SD) heart rate percent change from baseline values (ECG data).
- Overlay plot showing profiles of mean (SD) heart rate absolute change from baseline (first dose cardiac monitoring) and mean (SD) plasma concentration versus scheduled nominal time from start of treatment for Week 16 will be plotted by DB treatment. A similar set of overlay plots will also be generated instead using mean (SD) heart rate (beats/min) and mean (SD) heart rate percent change from baseline values (ECG data).
- A scatterplot of individual heart rate versus individual etrasimod plasma concentration from start of treatment for Day 1 and all scheduled nominal time by DB treatment, depicting regression relationship, will be generated; treatment groups will be denoted using different symbols but a single regression presented.

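### SAP 5.B gives two heart-rate references for Day 1 (last and lowest pre-dose) and only the last for Week 16, so within-arm first-dose changes may not be on the same footing

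*SAP*

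**What the plan says.** SAP 5.B (Definition of Baseline and Study Day) opens its double-blind bullet with a general rule: "baseline will be defined as the last available measurement prior to the first dose of the study drug in DB Treatment Period". For vital signs it then names the Day 1 pre-randomization assessments as baseline and continues: "The lowest pre-dose HR measurement will be used for comparison to the post-dose HR measurement". The bullet closes by labelling its content the DB baseline. Protocol 9.2.2 carries the same sentence on the lowest reading.

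For the extension, SAP 5.B says the OLE baseline "will be additionally defined as the last pre-dose measurement at Week 16". Protocol 11.9 agrees: "Baseline for the Open-Label Extension Period is defined as the last measurement prior to the first etrasimod dose started at Week 16". Neither shows an exception for heart rate.

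Two sets of outputs depend on these definitions.

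- SAP 9.E (Vital Signs): "At baseline and week 16, descriptive statistics for pre-dose measurements and change of vital signs values will be presented by treatment group", with a redaction before the words that place this after treatment initiation. It also says: "For OLE Period, change from Baseline will be calculated for the DB baseline and OLE baseline separately".
- SAP Appendix 1.D (Exposure-Response Relationship Analysis): overlay plots of "mean (SD) heart rate absolute change from baseline (first dose cardiac monitoring) and mean (SD) plasma concentration versus scheduled nominal time", one for Day 1 and one for Week 16. The list is introduced by the statement "Baseline below refers to DB Baseline".

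**The concern.** Protocol 1.3 describes a fall in heart rate on first dosing as an expected on-target class effect, greatest on the first day. Protocol 9.2.5 repeats cardiac monitoring when open-label etrasimod 2 mg starts. The size of the fall at each first dose is therefore a main safety description.

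The lowest of several readings is, on average, below the subject's usual resting level. Used as a baseline, it makes the fall look smaller, which is the non-conservative direction for safety. If Week 16 uses the last reading, the two first-dose changes differ by an amount that comes only from the definition. SAP 9 shows extension results by original double-blind group, and former placebo subjects take their first etrasimod at Week 16. A reader will naturally set their change beside that of the 2 mg arm on Day 1. The extension has no placebo arm to remove the shift.

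**Working it through.** The plan states no figure on this point, so there is none to reproduce.

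**Step 1: which reference each output uses, as written**

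| Output | Day 1 change from | Week 16 change from |
|---|---|---|
| SAP 9.E, OLE baseline for Week 16 | lowest or last pre-dose reading on Day 1 (5.B gives both) | last pre-dose reading at Week 16 |
| SAP 9.E, DB baseline for Week 16 | same | the Day 1 value |
| SAP Appendix 1.D overlay plots | same | the Day 1 value |

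A lowest-versus-last mismatch can arise only in the first row.

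**Step 2: direction.** Change from lowest = post − min(pre). Change from last = post − last(pre). The first minus the second is last(pre) − min(pre), which is never negative. A fall measured from the lowest reading is therefore equal to or smaller than the same fall measured from the last. With one reading the two coincide.

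**Step 3: size.** Assume k independent, normal pre-dose readings with no trend and within-session standard deviation SD. Then E[last − lowest] = c(k) × SD, where c(2) = 1/√π = 0.56 and c(3) = 3/(2√π) = 0.85. Simulation with 1,000,000 draws gave 0.564 and 0.845, and 1.028 for k = 4. Neither k nor SD is visible in the documents. At an assumed SD of 3 to 5 beats/min:

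- k = 1: 0
- k = 2: 0.564 × 3 = 1.7 to 0.564 × 5 = 2.8 beats/min
- k = 3: 0.845 × 3 = 2.5 to 0.845 × 5 = 4.2 beats/min

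**Step 4: illustration.** Assume a true fall of 10 beats/min on etrasimod, none on placebo, and SD 4.

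| | k = 2 | k = 3 |
|---|---|---|
| Etrasimod, Day 1, from lowest | −10 + 2.26 = −7.7 | −10 + 3.38 = −6.6 |
| Placebo, Day 1, from lowest | 0 + 2.26 = +2.3 | 0 + 3.38 = +3.4 |
| Etrasimod minus placebo, Day 1 | −10.0 | −10.0 |
| Same true fall at Week 16, from last | −10.0 | −10.0 |

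The shift is the same in every arm on Day 1 and cancels in the contrast. It remains in the within-arm change and in the comparison of Day 1 with Week 16.

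**Step 5: the Week 16 plot.** Under the opening statement of Appendix 1.D, the Week 16 profile is measured from the Day 1 value. Any drift in resting heart rate over about 16 weeks then enters the apparent first-dose effect. The documents give no figure from which to size that drift.

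**The case against.** The strongest case against is that the lowest reading may be a monitoring comparator and not a statistical baseline at all. In Protocol 9.2.2 the sentence naming the Day 1 vital signs as baseline is separate from the one on the lowest reading, and the next sentence points to cardiac monitoring and discharge criteria. The closing label in SAP 5.B could refer to the whole definition. Section 10.5.7.4 is redacted, and Protocol 9.2.5 sends Week 16 monitoring to the same section, so a matching heart-rate rule for Week 16 may exist there. All of this stands. It means the text is ambiguous, and it does not show which value the programmer should use.

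The size is also assumed. If heart rate settles with rest, the last reading may itself be the lowest and the gap shrinks toward zero. That stands too.

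The remaining outputs limit the harm. The Day 1 plots are drawn by treatment with placebo shown, absolute values are summarised and plotted, values are listed by subject, and the extension is descriptive only.

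Three stronger readings are tempting but unsupported.

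- A reader might infer that the Day 1 and Week 16 overlay plots mix the lowest and last readings. Appendix 1.D assigns the DB baseline to both.
- A reader might infer that the drug effect against placebo is understated. The shift cancels there.
- A reader might infer that percent falls are understated as well. SAP 9.E plans absolute values and change for vital signs. The percent change in Appendix 1.D is tagged as ECG data, and the visible text does not settle the baseline rule for ECG heart rate.

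**Conclusion.** The point holds as a definitional inconsistency with a small, conditional effect. SAP 5.B gives both last and lowest for Day 1 heart rate, and only last for Week 16. If the lowest is used on Day 1 and more than one reading is taken, the within-arm Day 1 fall in SAP 9.E is equal to or smaller than it would be under the Week 16 rule. The two first doses are then not comparable when the OLE baseline is used.

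The range of 1.7 to 4.2 beats/min rests on two or three independent, trend-free readings and an assumed SD of 3 to 5. It is zero with one reading. The documents do not establish that the Day 1 fall will in fact be understated, because the number of readings and Section 10.5.7.4 are hidden.

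The Week 16 plot in Appendix 1.D is a separate matter: its stated baseline predates that first dose by about 16 weeks. Neither point touches efficacy or the Day 1 comparison with placebo.

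**What to change.** In SAP 5.B, 9.E and Appendix 1.D, name one statistical heart-rate baseline for change summaries and plots at both Day 1 and Week 16: either the mean or the last of that day's pre-dose readings. Applying one rule on both days removes the definitional gap. Under the assumptions above, mean and last have the same expected value. Measure the Week 16 first-dose profile from the Week 16 pre-dose value. If change from the Day 1 value is also wanted, show it separately and label it.

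List the lowest pre-dose reading by subject. Record the change in SAP Section 11 as a clarification of Protocol 9.2.2, so that the two documents are reconciled. Leave any monitoring use of the lowest reading as it is; this proposal concerns only the statistical summaries.

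The cost is SAP wording and some programming on readings already collected. Where the lowest would otherwise have been used, reported within-arm Day 1 falls will be the same or, on average, slightly larger. If the primary database lock has passed, the SAP Introduction allows amendment for ad hoc analyses before the final lock, and the revised summaries should be labelled as such.

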9.2.4. Double-Blind Treatment Period Safety Follow-Up Visit

Subjects who complete the Double-Blind Treatment Period will return for a Safety Follow-Up Visit 4 weeks after the last dose of study treatment (Week 16). Visit assessments are detailed in the [REDACTED].

Subjects who terminate the study treatment early in the Double-Blind Treatment Period, should have an EoT Visit (Section 9.3) and a Safety Follow-Up Visit 4 weeks after the last dose of study treatment.

For subjects that have discontinued study treatment prior to Week 12 or are determined ineligible for the Open-Label Extension Period (Section 9.2.5), Week 16 will be the End of Study Visit (Section 9.4). Whenever possible, visits should be scheduled on the Weeks designated in the [REDACTED].

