9.3. Early Study Treatment Termination

Subjects who stop taking their study treatment before the end of the Double-Blind Treatment or Open-Label Extension Periods will return to the study site for an EoT Visit within 1 week of the last study treatment administration. Subjects who stop taking their study treatment before the end of the Double-Blind Treatment Period are not eligible to participate in the Open-Label Extension Period. Visit assessments are detailed in the [REDACTED]. Study site staff will work with subjects who withdraw early to obtain as much follow-up data as possible. Lymphocyte counts should be monitored until returned to approximately baseline or stable. In the Double-Blind Treatment Period, whenever possible, subjects should continue in the study even if study treatment has been discontinued. Subjects who discontinue study treatment, but who consent to remain in the study will continue to comply with study visits and assessments.

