10.5.7.3. Guidance on Monitoring Subjects for Infections

[REDACTED]

Therefore, investigators and subjects should be vigilant in monitoring for signs and symptoms of infections during the trial and after discontinuation of study treatment. Subjects should be instructed to promptly report to their treating physicians and investigator any signs and symptoms of infection (eg, fever, visualized red or swollen body parts). All infections that develop during the study will be reported as AEs on the respective eCRF pages ([Appendix 2](#)).

All infections that develop during the study will be reported as AEs on the respective eCRF pages. In the case of suspected or confirmed serious or atypical infection that is considered related to study treatment, study treatment interruption should be considered, and the Investigator should inform the medical monitor of any such cases. The elimination half-life of approximately 33 hours allows washout of etrasimod within a week.

Additional evaluations will be performed at the discretion of the Investigator and/or specialist consultants.

[REDACTED]

All radiologic images (eg, magnetic resonance imaging, computer tomography, x-rays) and diagnostic laboratory test results performed by local laboratories/facilities should be retained as source documents by study sites and made available upon request by the Sponsor for central adjudication as needed. All infections that develop during the study will be reported as AEs on the respective eCRF pages.

The Investigator should consider early treatment with specific antimicrobial therapy on the basis of clinical diagnosis or suspicion thereof (eg, antiviral treatment for herpes simplex or zoster) and may consult with infectious disease experts, as appropriate.

[REDACTED]

[REDACTED]

[REDACTED]

[REDACTED]

- [REDACTED]
- [REDACTED]
- [REDACTED]
- [REDACTED]
- [REDACTED]

[REDACTED]

[REDACTED]	[REDACTED]	[REDACTED]	[REDACTED]
[REDACTED]	[REDACTED]	[REDACTED]	[REDACTED]
[REDACTED]	[REDACTED]	[REDACTED]	[REDACTED]
[REDACTED]	[REDACTED]	[REDACTED]	[REDACTED]

[REDACTED]

- [REDACTED]

[REDACTED]

[REDACTED]
[REDACTED]
[REDACTED]
[REDACTED]

[REDACTED]

[REDACTED]

[REDACTED]

[REDACTED]

- [REDACTED]
- [REDACTED]
- [REDACTED]

- [REDACTED]

[Redacted text block]

[Redacted]
[Redacted]
[Redacted]

[Redacted text block]

[Redacted text block]

[Redacted text block]

[Redacted text block]

[REDACTED]

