Efficacy and safety endpoints will be analyzed according to their windowed visits defined by actual overall study day (i.e. calculated relative to first dose date in the DB Treatment Period). If more than one visit occurs within a single visit window, then the analysis will take the one closest to the target day. If the 2 visits are equidistant from the target day, the later visit will be used. Some efficacy or safety data are not scheduled to be assessed at each post-baseline visit. If the assessment date is not in the analysis visit window, the analysis will take the post-baseline scheduled visit closest to the assessment date. If there are 2 scheduled visits equidistant from the assessment date, the later visit will be used. The below table provides details of each analysis visit window.

D. Covariate Adjustment in Primary Analysis

The primary efficacy analyses will adjust for baseline EASI score, baseline vIGA score (3 versus 4) and region [REDACTED]. Key secondary analyses will adjust for baseline vIGA score (3 versus 4) and region [REDACTED] as described in Section 8 Efficacy Analyses below.

E. Interim Analyses

No formal interim analysis of efficacy is planned. Periodic blinded assessments may be conducted to assess the assumption regarding the SD of the percentage change in EASI from Baseline to Week 12. The planned sample size will not be reduced as a result of the SD assessments.

F. Multiple Comparisons and Multiplicity

For DB Treatment Period: no formal testing strategy or adjustments of the Type I error will be employed for the primary and key secondary endpoints. Estimates and confidence intervals (CIs) for treatment groups and from pairwise comparisons will be reported in an exploratory manner.

[figure not shown]
For the OLE Period: no formal statistical testing will be performed. Only descriptive statistics will be provided.

G. Analysis Sets

The following analysis sets will be defined for the DB Treatment Period and OLE Period separately:

Table 2 Analysis Sets

Analysis Set	Description
DB Treatment Period	
Full Analysis Set (FAS)	The FAS includes all randomized subjects, irrespective of whether they received any study treatment.

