Modified Full Analysis Set (mFAS)	The mFAS consists of all randomized subjects who received at least 1 dose of study treatment, have a baseline measurement, and have at least 1 post-randomization measurement. The mFAS is endpoint specific, therefore subjects included in the analysis set for 1 endpoint may differ from another endpoint, based on the baseline and post-baseline data.
Per Protocol Set (PPS)	The PPS consists of all subjects in the FAS who adhere to the protocol. The PPS will be used in sensitivity analyses of the primary and key secondary endpoints to evaluate the influence of major protocol violators and protocol deviators on the primary results. Specific reasons for warranting exclusion from this analysis set will be documented prior to database lock and may include, but are not limited to: 
 • Not meeting critical inclusion/exclusion criteria • Study treatment noncompliance • Receiving incorrect study treatment • Missing more than a defined number of visits while still on study • Chronic prohibited medication use while on study treatment
Treatment Completer Set (TCS)	The TCS includes subjects in EASI or vIGA specific mFAS who have completed 12 weeks of study treatment in DB Treatment Period.
Safety Set (SAF)	The SAF includes all randomized subjects who received at least 1 dose of study treatment.
[REDACTED]	[REDACTED]
Post Hoc Analyses Set (PHAS)	The PHAS excludes 9 subjects from the Full Analyses Set in the 2 mg treatment group with unwarranted dose interruption due to lymphocyte decrease between week 4 and 12
OLE Period	
OLE Safety Set (OLE SAF)	The OLE SAF includes all subjects who enrolled in the OLE Period and received at least one dose of etrasimod. All safety

	
and efficacy analysis in the OLE Period will be performed over OLE SAF. For the analyses of efficacy endpoints, subjects will further be required to have at least one efficacy measurement in the OLE Period. Therefore, efficacy evaluable set is endpoint specific.

H. Missing Data

In order to analyze primary and secondary efficacy endpoints at Week 12 in the FAS, the handling of missing data and rescue medication uses are specified in Section 8.B - 8.C. No imputation will be implemented for exploratory efficacy and safety endpoints. The handling of missing reporting information for safety assessments are specified in Section 9.

I. Data Display Characteristics

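### By-visit laboratory summaries do not separate on-drug from off-drug values, so the lymphocyte effect after Week 4, chiefly at 2 mg, can be understated

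*SAP*

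**What the plan says.** **Visit assignment.** SAP 5.C: "Efficacy and safety endpoints will be analyzed according to their windowed visits defined by actual overall study day", counted from the first double-blind dose. If two visits share a window, "then the analysis will take the one closest to the target day". For an assessment outside any window, "the analysis will take the post-baseline scheduled visit closest to the assessment date". None of these rules mentions dosing status.

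**Summaries.** SAP 9 uses the Safety Set, and Protocol 11.5 analyses safety by actual treatment. SAP 9.D: "Laboratory parameters from the central laboratory will be summarized by treatment group at each scheduled assessment time point", with shift tables at each post-baseline visit.

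**Off-drug values are collected on purpose.** Protocol 9.3: "Subjects who discontinue study treatment, but who consent to remain in the study will continue to comply with study visits and assessments". The same section has lymphocyte counts followed until they are near baseline or stable. Under Protocol 9.2.4, early stoppers "should have an EoT Visit (Section 9.3) and a Safety Follow-Up Visit 4 weeks after the last dose of study treatment".

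**Interruptions occurred.** SAP 5.G, Table 2, defines a post hoc set that leaves out nine 2 mg subjects with "unwarranted dose interruption due to lymphocyte decrease between week 4 and 12". SAP 12.A describes the same nine but places the interruption between Weeks 4 and 8.

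**Washout.** Protocol 10.5.7.3: "The elimination half-life of approximately 33 hours allows washout of etrasimod within a week".

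**The concern.** Protocol 10.2.7 treats lymphocyte lowering as a known pharmacodynamic effect, and the by-visit tables are where its size at each dose would be read. The nine interrupted subjects were picked out by that same laboratory effect, all in one arm. If their counts have partly recovered by a scheduled visit, they enter the 2 mg column at that visit with nothing to mark them. The 2 mg versus placebo difference then shrinks at those visits, and so does the 2 mg versus 1 mg contrast.

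The plan already treats these interruptions as important for efficacy: SAP 12.A repeats efficacy analyses without the nine. No visible safety summary has a counterpart. SAP 3.F makes incidence and severity of laboratory abnormalities a safety endpoint, but the visible part of 9.D plans no worst on-treatment value.

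**Working it through.** **1. The plan's own figure.** The half-life is about 33 hours (Protocol 10.5.7.3). Five half-lives are 5 × 33/24 = 6.9 days. At 7 days, 7 × 24/33 = 5.1 half-lives have passed and 2^(-5.1) = 2.9% of drug remains. Washout within a week reproduces. This is drug elimination and does not show that lymphocytes recover in a week.

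**2. Can an off-drug value reach a Week 1-12 row?** Yes, in three ways.
- A subject in an interruption attends the scheduled visit.
- A subject who has stopped attends the scheduled visit under Protocol 9.3.
- An early stopper's follow-up visit falls among the treatment weeks. If the last dose is on Day 28, that visit is due on Day 28 + 28 = Day 56. By study day this is closest to Week 8 among the visits in SAP 4.E (Weeks 1, 2, 4, 6, 8, 12, 16). It competes there with the subject's own Week 8 visit, which is also off drug; only one of the two is used.

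**3. Size.** Let E be the mean on-drug effect, f the share of subjects with a value at the visit who are off drug, and r the share of the effect they retain. The reported mean is

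(1 - f)E + f·r·E = E[1 - f(1 - r)], so the dilution is f(1 - r).

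Inputs: 9 interrupted subjects (SAP Table 2); 40 planned per arm (SAP 4.C). The values of r and the case of 3 subjects off drug are assumptions.

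| Off drug at the visit | f | r | Dilution f(1 - r) |
|---|---|---|---|
| none | 0 | any | 0 |
| 3 of 40 | 0.075 | 0 | 7.5% |
| 9 of 40 | 0.225 | 0.5 | 11.3% |
| 9 of 40 | 0.225 | 0 | 22.5% |

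The last row is the ceiling for the nine under this formula. The formula takes all 40 to have a value at the visit, and the off-drug subjects to have had the arm's average effect while on drug.

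**4. Which visits.** Table 2 (Weeks 4 to 12) puts the Week 6, 8 and 12 rows in question. SAP 12.A (Weeks 4 to 8) points to Weeks 6 and 8. The two statements conflict, so the documents do not settle whether Week 12 is affected.

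**The case against.** Summarising every Safety Set value by visit is a legitimate convention. SAP 4.E itself counts four drug-free weeks in the double-blind period, and nothing visible labels the rows as on-treatment. Other displays keep the effect in view: minima and maxima, shift tables at visits before any interruption, listings of all laboratory values with out-of-range results marked, adverse events by maximum CTCAE grade, and counts of interruptions. The window table and parts of the safety text are not shown and could contain a dosing rule. This all stands, and it makes the point a gap rather than an error. Listings and maximum grades still do not give an arm-level estimate of the on-drug laboratory effect by visit.

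Four stronger readings are tempting, and the documents support none of them.
- *Known effects are understated, as a fact.* This needs the number off drug at each visit, the length of interruption and the speed of lymphocyte recovery. None is given.
- *Heart rate is diluted in the same way.* Protocol 1.3 describes the reduction as greatest on the first dosing day with recovery afterwards, and SAP 9.E has a separate summary after treatment initiation.
- *The 25% drop-out allowance measures the off-drug share.* It is a sample-size allowance. Using it here would require all those who drop out to keep attending.
- *Recovery is lost from the Week 16 row.* Protocol 9.2.4 makes Week 16 the End of Study Visit for those who stopped before Week 12, so those who remain still supply a value there.

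A 7-day margin after the last dose can also be criticised, since only about 3% of drug is left by its end. That is fair. The margin is an analysis convention, and a shorter one would serve if stated in advance.

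**Conclusion.** The point holds as a gap in the visible plan. Safety values are placed by study day with no dosing condition, off-drug values are deliberately collected, and nine 2 mg subjects were interrupted because of the laboratory effect being summarised. By-visit laboratory means and shift tables after Week 4 can therefore understate the on-drug effect, most clearly for lymphocytes at 2 mg.

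The dilution of the mean due to the nine lies between 0 and 22.5% under the assumptions in the working. The upper end needs all nine to be off drug, attending and fully recovered at the same visit. Because they were selected for lymphocyte decrease, their on-drug effect may have been larger than average. The loss would then exceed f(1 - r) by an amount the documents do not allow one to compute. Adding on-treatment displays is a cheap improvement worth making.

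**What to change.** In SAP 5.C and 9.D:

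- Keep the all-data by-visit tables as planned.
- Define an on-treatment flag from last-dose and interruption dates, for example values up to 7 days after the last dose taken, stated as an analysis convention. Apply the same rule within interruptions.
- Add on-treatment by-visit summaries, worst on-treatment values and shift tables for laboratory parameters, at least lymphocytes and liver enzymes. The worst value matters because it keeps an interrupted subject's values from before the pause.
- Show an early stopper's 4-week Safety Follow-Up Visit in its own row rather than in a Week 1-12 window, unless the window table already does so.
- Reconcile the interruption period in SAP Table 2 (Weeks 4 to 12) with SAP 12.A (Weeks 4 to 8), since this decides which visits are affected.

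The cost is a few sentences, one derived flag from dosing dates already collected, and some extra tables. If added after the primary database lock, SAP section 1 requires these to be labelled ad hoc. The drawback is that late on-treatment rows hold fewer subjects, selected for having stayed on drug; the retained all-data tables offset this.
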